Table 11.7	Analysis of Self-reported hours of oxygen.....	21

Table 12	Adverse events (PP and ITT)	22
Table 12.1	Adverse events.....	22
Table 12.2	Time to adverse events.....	22
2	Figures.....	23
Figure 1	Kaplan-Meier figures for inclusion over time	23
Figure 1.1	Kaplan -Meier figure for inclusion over time (all randomized patients)	24
Figure 1.2	Kaplan -Meier figure for inclusion over time (by treatment group)	24
Figure 1.3	Kaplan -Meier figure for inclusion over time (by site).....	24
Figure 1.4	Cumulative enrollment over time in the study (all randomized patients).....	25
Figure 1.5	Cumulative enrollment over time in the study (by treatment).....	23
Figure 1.6	Cumulative enrollment over time in the study (by site)	23
Figure 1.7	Histogram with number of included patients by site and by treatment group	24
Figure 1.8	Reasons why the screened patients were not included in the study.....	25
Figure 1.9	Kaplan-Meier figure: Time from start until the patient stops being treated	25
Figure 2	CONSORT flow chart	26
Figure 3	Cumulative hazard by treatment.....	27
Figure 3.1	Primary outcome (ITT)	27
Figure 4	HR with non-superiority limit for the primary endpoint	28
3	Listings	29
Listing 1	Patient disposition	29
Listing 2	Demographics and characteristics at screening visit.....	29
Listing 3	Time of randomization to death or censoring.....	29
Listing 4	Patients withdrawal	29
Listing 5	Patients discontinuing LTOT	29
Listing 6	Time of randomization to hospitalization or censoring	29
Listing 7	Subjects excluded from the ITT and PP	29
Listing 8	Screening failures.....	29
Listing 9	Adverse events.....	29
Listing 10	Loss to follow-up for the composite endpoint of death or 1 st hospitalization.....	29
Listing 11	Study termination (End of study)	29

1 Tables

The most of the tables will be presented by ITT, PP, subgroups and at 3 and 12 months, where applicable.

The subgroups mentioned in this plan are corresponding to following definitions:

Subgroup 1= Patients with more severe resting hypoxemia (PaO₂ < 7.4 kPa on air) at LTOT start

Subgroup 2= Patients with more moderate hypoxemia (PaO₂ 7.4–8.0 kPa on air) at LTOT start

Subgroup 3= Patients with verified COPD (FEV₁/FVC < 0.7 after bronchodilation)

Subgroup 4= Patients with primary diagnosis other than COPD

Table 1 Subject disposition

	Treatment group		Total n
	LTOT 24h/day n	LTOT 15h/day n	
Patients screened /enrolled			x
Patients randomized in the study	x	x	x
Patients completed the study, n(%)*	x(x)	x (x)	x (x)
Patients discontinued LTOT, n (%)*	x(x)	x (x)	x (x)
- due to x**	x(x)	x (x)	x (x)
- due to xx**	x(x)	x (x)	x (x)
- due to xxx**	x(x)	x (x)	x (x)
Patients withdrawn from the study, n(%)*	x (x)	x (x)	x (x)
- due to x**	x(x)	x (x)	x (x)
- due to xx**	x(x)	x (x)	x (x)
- due to xxx**	x(x)	x (x)	x (x)
Patients included in Safety population***	x(x)	x (x)	x (x)
Patients included in Intention to Treat (ITT) population*	x(x)	x (x)	x (x)
Patients included in Per Protocol (PP) population*	x(x)	x (x)	x (x)
Patients with more severe resting hypoxemia at LTOT start *	x(x)	x(x)	x(x)
Patients with more moderate hypoxemia at LTOT start *	x(x)	x(x)	x(x)
Patients with verified COPD*	x(x)	x(x)	x(x)
Patients with other conditions than COPD*	x(x)	x(x)	x(x)

*the denominator is the number of randomized patients

** the denominator is the number of withdrawn patients

***If there are no incorrectly randomized patients or patients who started the wrong treatment, the safety population will be the same as the ITT population.

Table 2 Reason for exclusion from analysis sets

Based on the number of randomized subjects

	LTOT 24h/day	LTOT 15h/day	Total
	n	n	n
Number of excluded from Intention to Treat (ITT)	x	x	x
Reason for Exclusion from Intention to Treat (ITT)			
- due to x*	x(x)	x(x)	x(x)
- due to xx*	x(x)	x(x)	x(x)
- due to xxx etc..	x(x)	x(x)	x(x)
Number of excluded from Per Protocol Analysis Set (PP)	x	x	x
Reason for Exclusion from Per Protocol Analysis Set (PP)			
- due to x*	x(x)	x(x)	x(x)
- due to xx*	x(x)	x(x)	x(x)
- due to xxx etc..	x(x)	x(x)	x(x)
Number of excluded from Subgroup 1	x	x	x
Reason for Exclusion from Subgroup 1			
- due to x*	x(x)	x(x)	x(x)
- due to xx*	x(x)	x(x)	x(x)
- due to xxx etc..	x(x)	x(x)	x(x)
Number of excluded from Subgroup 2	x	x	x
Reason for Exclusion from Subgroup 2			
- due to x*	x(x)	x(x)	x(x)
- due to xx*	x(x)	x(x)	x(x)
- due to xxx etc..	x(x)	x(x)	x(x)
Number of excluded from Subgroup 3	x	x	x
Reason for Exclusion from Subgroup 3			
- due to x*	x(x)	x(x)	x(x)
- due to xx*	x(x)	x(x)	x(x)

- due to xxx etc..	x(x)	x(x)	x(x)
Number of excluded from Subgroup 4	x	x	x
Reason for Exclusion from Subgroup 4			
- due to x*	x(x)	x(x)	x(x)
- due to xx*	x(x)	x(x)	x(x)
- due to xxx etc..	x(x)	x(x)	x(x)

 Table 3 **Protocol deviations**

NOTE: This table will be created if there is enough data. Otherwise, protocol deviations will be presented in a listing

Protocol deviations	LTOT 24h/day n	LTOT 15h/day n	Total n
Number of protocol deviations	x	x	x
Protocol deviations Categories			
xxx	x(%)	x(%)	x(%)
xxx	x(%)	x(%)	x(%)
xxx	x(%)	x(%)	x(%)
xxx	x(%)	x(%)	x(%)
Etc.	x(%)	x(%)	x(%)

*Denominator is number of major protocol deviation

Table 4 Number of patients by randomizing center

Center	Number of screened patients n	Number of included patients n	Number of included patients n(%)*	Number of patients included in ITT population n	Number of patients included in PP population n	Number of patients included in subgroup= Patients with more severe resting hypoxemia at LTOT start	Number of patients included in subgroup= Patients with more moderate hypoxemia at LTOT start	Number of patients included in subgroup= Patients with verified COPD	Number of patients included in subgroup= Patients with other conditions than COPD
Falun									
Göteborg									
Malmö									
Etc...									
All sites									

*Denominator in the number of screened patients

Table 4.1 Number of patients by randomizing center: treatment group: LTOT 24h/day

Similar table as table above

Table 4.2 Number of patients by randomizing center: treatment group: LTOT 15h/day

Similar table as table above

Table 5 Time from randomization to death/hospitalization or censoring

Time to event = time from randomization to (death / hospitalization) / time from randomization to censoring

First and last inclusion date will be presented

Table 5.1 ITT

	Variable	N	Mean	Median	IQR	Minimum	Maximum
LTOT 24h/day	Time to death	xx	xx.x	xx.x	xx.x	xx	xx
	Time to first hospitalization	xx	xx.x	xx.x	xx.x	xx	xx
	Time to Composite	xx	xx.x	xx.x	xx.x	xx	xx
LTOT 15h/day	Time to death	xx	xx.x	xx.x	xx.x	xx	xx
	Time to Hospitalization	xx	xx.x	xx.x	xx.x	xx	xx
	Time to Composite	xx	xx.x	xx.x	xx.x	xx	xx
Total	Time to death	xx	xx.x	xx.x	xx.x	xx	xx
	Time to Hospitalization	xx	xx.x	xx.x	xx.x	xx	xx
	Time to Composite	xx	xx.x	xx.x	xx.x	xx	xx

Table 5.2 At 3 months (PP)

Table 5.3 At 3 months (Subgroup 1)

Table 5.4 At 3 months (Subgroup 2)

Table 5.5 At 3 months (Subgroup 3)

Table 5.6 At 3 months (Subgroup 4)

Table 5.7 At 12 months (ITT)

Table 5.8 At 12 months (PP)

Table 5.9 At 12 months (Subgroup 1)

Table 5.10 At 12 months (Subgroup 2)

Table 5.11 At 12 months (Subgroup 3)

Table 5.12 At 12 months (Subgroup 4)

Table 5.13 Event rate at 3 months (ITT)

	Statistics	LTOT 24h/day	LTOT 15h/day	Total
Composite (All-cause mortality/ All-cause Hospitalization)	Number of patients	xx	xx	xx
	Number of events	xx	xx	xx
	Person-years	xxx	xxx	xxx
	Events/Participants	xx.x	xx.x	xx.x
	Event rate per 100 patient-years (95% CI)	xx.x	xx.x	xx.x
	HR (95% CI) - p-value	xx.x (x.xx-x.xx) – 0.xxxx		
All-cause Hospitalization	Number of patients	xx	xx	xx
	Number of events	xx	xx	xx
	Number of competing events	xx	xx	xx
	Person-years	xxx	xxx	xxx
	Events/Participants	xx.x	xx.x	xx.x
	Event rate per 100 patient-years (95% CI)	xx.x	xx.x	xx.x
All-cause mortality	Number of patients	xx	xx	xx
	Number of events	xx	xx	xx
	Person-years	xxx	xxx	xxx
	Events/Participants	xx.x	xx.x	xx.x
	Event rate per 100 patient-years (95% CI)	xx.x	xx.x	xx.x
	HR (95% CI) - p-value	xx.x (x.xx-x.xx) – 0.xxxx		
Mortality from respiratory disease	Number of patients	xx	xx	xx
	Number of events	xx	xx	xx
	Person-years	xxx	xxx	xxx
	Events/Participants	xx.x	xx.x	xx.x
	Event rate per 100 patient-years (95% CI)	xx.x	xx.x	xx.x
	HR (95% CI) - p-value	xx.x (x.xx-x.xx) – 0.xxxx		
Mortality from cardiovascular disease	Number of patients	xx	xx	xx
	Number of events	xx	xx	xx
	Person-years	xxx	xxx	xxx

	Statistics	LTOT 24h/day	LTOT 15h/day	Total
	Events/Participants	xx.x	xx.x	xx.x
	Event rate per 100 patient-years (95% CI)	xx.x	xx.x	xx.x
	HR (95% CI) - p-value	xx.x (x.xx-x.xx) – 0.xxxx		
Hospitalization from respiratory disease	Number of patients	xx	xx	xx
	Number of events	xx	xx	xx
	Number of competing events	xx	xx	xx
	Person-years	xxx	xxx	xxx
	Events/Participants	xx.x	xx.x	xx.x
	Event rate per 100 patient-years (95% CI)	xx.x	xx.x	xx.x
	HR (95% CI) - p-value	xx.x (x.xx-x.xx) – 0.xxxx		
Hospitalization from cardiovascular disease	Number of patients	xx	xx	xx
	Number of events	xx	xx	xx
	Number of competing events	xx	xx	xx
	Person-years	xxx	xxx	xxx
	Events/Participants	xx.x	xx.x	xx.x
	Event rate per 100 patient-years (95% CI)	xx.x	xx.x	xx.x
	HR (95% CI) - p-value	xx.x (x.xx-x.xx) – 0.xxxx		

- Table 5.14 Event rate at 3 months (PP)
- Table 5.15 Event rate at 3 months (Subgroup 1)
- Table 5.16 Event rate at 3 months (Subgroup 2)
- Table 5.17 Event rate at 3 months (Subgroup 3)
- Table 5.18 Event rate at 3 months (Subgroup 4)
- Table 5.19 Event rate at 12 months (ITT)
- Table 5.20 Event rate at 12 months (PP)
- Table 5.21 Event rate at 12 months (Subgroup 1)
- Table 5.22 Event rate at 12 months (Subgroup 2)
- Table 5.23 Event rate at 12 months (Subgroup 3)
- Table 5.24 Event rate at 12 months (Subgroup 4)

Table 6 Demographics and characteristics at baseline

Table 6.1 ITT

Variable	Statistics	LTOT 24h/day n	LTOT 15h/day n	Total n	*P-value
Age (years)	n	x	x	x	0.xxx
	Mean (SD)	x (x)	x (x)	x (x)	
	Median (IQR)	x (x)	x (x)	x (x)	
	Missing	x	x	x	
Sex	Male, n (%)	x (x)	x (x)	x (x)	0.xxx
	Female, n (%)	x (x)	x (x)	x (x)	
	Missing	x (x)	x (x)	x (x)	
Height	n	x	x	x	0.xxx
	Mean (SD)	x (x)	x (x)	x (x)	
	Median (IQR)	x (x)	x (x)	x (x)	
	Missing	x	x	x	
Weight	n	x	x	x	0.xxx
	Mean (SD)	x (x)	x (x)	x (x)	
	Median (IQR)	x (x)	x (x)	x (x)	
	Missing	x	x	x	
Body Mass Index (BMI)	n	x	x	x	0.xxx
	Mean (SD)	x (x)	x (x)	x (x)	
	Median (IQR)	x (x)	x (x)	x (x)	
	Missing	x	x	x	
Smoking status	Never smoked	x (x)	x (x)	x (x)	0.xxx
	Former smoker	x (x)	x (x)	x (x)	
	Current smoker	x (x)	x (x)	x (x)	
	Unknown	x (x)	x (x)	x (x)	
Performance status	Can handle normal activity (WHO 0)	x (x)	x (x)	x (x)	0.xxx
	Symptoms but almost completely recovered (WHO 1)	x (x)	x (x)	x (x)	
	Confined to bed (<50% of daytime) (WHO 2)	x (x)	x (x)	x (x)	
	Staying in bed (>50% of daytime) (WHO 3)	x (x)	x (x)	x (x)	
	Unable to get out of bed (WHO 4)	x (x)	x (x)	x (x)	
	Missing	x (x)	x (x)	x (x)	
Primary diagnosis	COPD	x (x)	x (x)	x (x)	0.xxx
	Emphysema	x (x)	x (x)	x (x)	

Variable	Statistics	LTOT 24h/day n	LTOT 15h/day n	Total n	*P-value
Other respiratory disease	Other respiratory disease	x (x)	x (x)	x (x)	
	Pulmonary fibrosis	x (x)	x (x)	x (x)	
	Sarcoidosis	x (x)	x (x)	x (x)	
	Other parenchymal disease	x (x)	x (x)	x (x)	
	Hypertension	x (x)	x (x)	x (x)	
	Chronic pulmonary embolism	x (x)	x (x)	x (x)	
	Other pulmonary vascular disease	x (x)	x (x)	x (x)	
	Heart disease	x (x)	x (x)	x (x)	
	Thoracic deformity	x (x)	x (x)	x (x)	
	Hypoventilation	x (x)	x (x)	x (x)	
	Tumor in lung or pleura	x (x)	x (x)	x (x)	
	Other	x (x)	x (x)	x (x)	
Secondary diagnosis	COPD	x (x)	x (x)	x (x)	0.xxx
	Emphysema	x (x)	x (x)	x (x)	
	Other respiratory disease	x (x)	x (x)	x (x)	
	Pulmonary fibrosis	x (x)	x (x)	x (x)	
	Sarcoidosis	x (x)	x (x)	x (x)	
	Other parenchymal disease	x (x)	x (x)	x (x)	
	Hypertension	x (x)	x (x)	x (x)	
	Chronic pulmonary embolism	x (x)	x (x)	x (x)	
	Other pulmonary vascular disease	x (x)	x (x)	x (x)	
	Heart disease	x (x)	x (x)	x (x)	
	Thoracic deformity	x (x)	x (x)	x (x)	
	Hypoventilation	x (x)	x (x)	x (x)	
Liquid oxygen	Yes	x (x)	x (x)	x (x)	0.xxx
	No	x (x)	x (x)	x (x)	
	Unknown	x (x)	x (x)	x (x)	
Oxygen concentrator	Yes	x (x)	x (x)	x (x)	0.xxx
	No	x (x)	x (x)	x (x)	
	Unknown	x (x)	x (x)	x (x)	
Portable oxygen	Yes	x (x)	x (x)	x (x)	0.xxx
	No	x (x)	x (x)	x (x)	

Variable	Statistics	LTOT 24h/day n	LTOT 15h/day n	Total n	*P-value
	Unknown	x (x)	x (x)	x (x)	
Type of portable oxygen	Liquid oxygen	x (x)	x (x)	x (x)	0.xxx
	Oxygen tubes	x (x)	x (x)	x (x)	
	Portable concentrator	x (x)	x (x)	x (x)	
	Unknown	x (x)	x (x)	x (x)	
Prescribed oxygen flow rate (l/min)	n	x	x	x	0.xxx
	Mean (SD)	x (x)	x (x)	x (x)	
	Median (IQR)	x (x)	x (x)	x (x)	
	Missing	x	x	x	
Prescribed treatment duration (hours/day)	n	x	x	x	0.xxx
	Mean (SD)	x (x)	x (x)	x (x)	
	Median (IQR)	x (x)	x (x)	x (x)	
	Missing	x	x	x	
PO2 air	n	x	x	x	0.xxx
	Mean (SD)	x (x)	x (x)	x (x)	
	Median (IQR)	x (x)	x (x)	x (x)	
	Missing	x	x	x	
PCO2 air	n	x	x	x	0.xxx
	Mean (SD)	x (x)	x (x)	x (x)	
	Median (IQR)	x (x)	x (x)	x (x)	
	Missing	x	x	x	
SPO2 air	n	x	x	x	0.xxx
	Mean (SD)	x (x)	x (x)	x (x)	
	Median (IQR)	x (x)	x (x)	x (x)	
	Missing	x	x	x	
PO2 oxygen	n	x	x	x	0.xxx
	Mean (SD)	x (x)	x (x)	x (x)	
	Median (IQR)	x (x)	x (x)	x (x)	
	Missing	x	x	x	
PCO2 oxygen	n	x	x	x	0.xxx
	Mean (SD)	x (x)	x (x)	x (x)	
	Median (IQR)	x (x)	x (x)	x (x)	
	Missing	x	x	x	
SPO2 oxygen	n	x	x	x	0.xxx

Variable	Statistics	LTOT 24h/day n	LTOT 15h/day n	Total n	*P-value
	Mean (SD)	x (x)	x (x)	x (x)	
	Median (IQR)	x (x)	x (x)	x (x)	
	Missing	x	x	x	
FEV1	n	x	x	x	0.xxx
	Mean (SD)	x (x)	x (x)	x (x)	
	Median (IQR)	x (x)	x (x)	x (x)	
	Missing	x	x	x	
FVC	n	x	x	x	0.xxx
	Mean (SD)	x (x)	x (x)	x (x)	
	Median (IQR)	x (x)	x (x)	x (x)	
	Missing	x	x	x	
Concurrent treatment with home bilevel PAP (bilevel positive airway pressure)	n	x	x	x	0.xxx
	Mean (SD)	x (x)	x (x)	x (x)	
	Median (IQR)	x (x)	x (x)	x (x)	
	Missing	x	x	x	

* The treatment groups chi-square test statistic for categorical variables and the Wilcoxon's test statistic for numerical data using observed cases

- Table 6.2 PP
- Table 6.3 Subgroup 1
- Table 6.4 Subgroup 2
- Table 6.5 Subgroup 3
- Table 6.6 Subgroup 4

Table 7 External validity

Aggregated data for the complete Swedevox LTOT cohort for same time period (first to last patient randomized) will be compared to study data. A table with baseline characteristics (as in table 6) such as age, gender, smoking, BMI etc. will be constructed. Proportion randomized patients among these will be presented.

Table 8 Number of days of treatment

*This table shows the total LTOT duration (number of days)

Population	Statistics	LTOT Duration of treatment	
		LTOT 24h/day n	LTOT 15h/day n
ITT	n		
	Mean (SD)		
	Median (IQR)		
	Min-Max		
PP	n		
	Mean (SD)		
	Median (IQR)		
	Min-Max		
Subgroup 1	n		
	Mean (SD)		
	Median (IQR)		
	Min-Max		
Subgroup 2	n		
	Mean (SD)		
	Median (IQR)		
	Min-Max		
Subgroup 3	n		
	Mean (SD)		
	Median (IQR)		
	Min-Max		
Subgroup 4	n		
	Mean (SD)		
	Median (IQR)		
	Min-Max		

Table 9 Description of outcomes

The table below shows the descriptive data by treatment group for each outcome.

Table 9.1 ITT

	Outcome	Statistics	LTOT 24h/day n	LTOT 15h/day n	Total n
At 3 months	All-cause mortality	n(%)			
	All-cause Hospitalization	n(%)			
	Composite (All-cause mortality/ All-cause Hospitalization)	n(%)			
	Mortality from respiratory disease	n(%)			
	Mortality from cardiovascular disease	n(%)			
	Hospitalization from respiratory disease	n(%)			
	Hospitalization from cardiovascular disease	n(%)			
	Self-reported hours of oxygen* (within 24 hours)	n Mean (SD) Median (IQR) Min-Max			
At 12 months	All-cause mortality	n(%)			
	All-cause Hospitalization	n(%)			
	Composite (All-cause mortality/ All-cause Hospitalization)	n(%)			
	Mortality from respiratory disease	n(%)			
	Mortality from cardiovascular disease	n(%)			
	Hospitalization from respiratory disease	n(%)			
	Hospitalization from cardiovascular disease	n(%)			
	Self-reported hours of oxygen* (within 24 hours)	n Mean (SD) Median (IQR) Min-Max			

* Self-reported oxygen use is defined as mean hours/day. If missing, we will use mean h/day last week, using the questionnaire at 12 months, or (if missing) 3 months.

Table 9.2 PP

Table 9.3 Subgroup 1

Table 9.4 Subgroup 2

Table 9.5 Subgroup 3

Table 9.6 Subgroup 4

Table 10 Analysis of the primary variable

Table 10.1 Primary outcome

Population	Outcome	Reference group	HR (90% CI)	p-value*	p-value**
ITT	Composite event of death or 1 st hospitalization at 1 year	LTOT 15h/day	x.xx (x.xx-x.xx)	x.xx	x.xxx
PP	Composite event of death or 1 st hospitalization at 1 year	LTOT 15h/day	x.xx (x.xx-x.xx)	x.xx	x.xxx

*The p-value for the difference between treatments H0: HR=1

** The p-value corresponds to the one-sided test, at 5% significance level, that the lower limit exceeds the hypothesized value 0.67

Table 10.2 Primary outcome adjusted for sex and age

Similar table as in 10.1 repeated adjusting for sex and age (in years) at randomization. A frailty model will be performed with “center” as a random effect to account for the clustering by hospital.

Table 11 Analyses of secondary variables

Table 11.1 Secondary outcome (ITT)

Population	Outcome	Reference group	n events/competing events	HR (90% CI)	p-value*	p-value**
At 3 months	Composite event of death or 1 st hospitalization	LTOT 15h/day	xx	x.xx (x.xx-x.xx)	x.xx	x.xxx
	All-cause mortality	LTOT 15h/day	xx	x.xx (x.xx-x.xx)	x.xx	x.xxx
	All-cause Hospitalization***	LTOT 15h/day	xx/xx	x.xx (x.xx-x.xx)	x.xx	x.xxx
	Mortality from respiratory disease	LTOT 15h/day	xx	x.xx (x.xx-x.xx)	x.xx	x.xxx
	Mortality from cardiovascular disease	LTOT 15h/day	xx	x.xx (x.xx-x.xx)	x.xx	x.xxx
	Hospitalization from respiratory disease***	LTOT 15h/day	xx/xx	x.xx (x.xx-x.xx)	x.xx	x.xxx
	Hospitalization from cardiovascular disease***	LTOT 15h/day	xx/xx	x.xx (x.xx-x.xx)	x.xx	x.xxx
At 1 year	All-cause mortality	LTOT 15h/day	xx	x.xx (x.xx-x.xx)	x.xx	x.xxx
	All-cause Hospitalization ***	LTOT 15h/day	xx/xx	x.xx (x.xx-x.xx)	x.xx	x.xxx
	Mortality from respiratory disease	LTOT 15h/day	xx	x.xx (x.xx-x.xx)	x.xx	x.xxx

	Mortality from cardiovascular disease	LTOT 15h/day	xx/xx	x.xx (x.xx-x.xx)	x.xx	x.xxx
	Hospitalization from respiratory disease***	LTOT 15h/day	xx/xx	x.xx (x.xx-x.xx)	x.xx	x.xxx
	Hospitalization from cardiovascular disease***	LTOT 15h/day	xx	x.xx (x.xx-x.xx)	x.xx	x.xxx

*** Hospitalizations are analyzed using Fine Gray regression accounting for death as competing event

Table 11.2 Secondary outcome (PP)

Table 11.3 Secondary outcome (Subgroup 1)

Table 11.4 Secondary outcome (Subgroup 2)

Table 11.5 Secondary outcome (Subgroup 3)

Table 11.6 Secondary outcome (Subgroup 4)

Table 11.7 Analysis of Self-reported hours of oxygen

Similar table as in 10.1

	Population	Outcome	Mean difference (95% CI)	p-value**
At 3 months	ITT	Self-reported hours of oxygen* (within 24 hours)	x.xx (x.xx-x.xx)	x.xx
	PP	Self-reported hours of oxygen* (within 24 hours)	x.xx (x.xx-x.xx)	x.xx
	Subgroup 1	Self-reported hours of oxygen* (within 24 hours)	x.xx (x.xx-x.xx)	x.xx
	Subgroup 2	Self-reported hours of oxygen* (within 24 hours)	x.xx (x.xx-x.xx)	x.xx
	Subgroup 3	Self-reported hours of oxygen* (within 24 hours)	x.xx (x.xx-x.xx)	x.xx
	Subgroup 4	Self-reported hours of oxygen* (within 24 hours)	x.xx (x.xx-x.xx)	x.xx
At 1 year	ITT	Self-reported hours of oxygen* (within 24 hours)	x.xx (x.xx-x.xx)	x.xx
	PP	Self-reported hours of oxygen* (within 24 hours)	x.xx (x.xx-x.xx)	x.xx
	Subgroup 1	Self-reported hours of oxygen* (within 24 hours)	x.xx (x.xx-x.xx)	x.xx
	Subgroup 2	Self-reported hours of oxygen* (within 24 hours)	x.xx (x.xx-x.xx)	x.xx
	Subgroup 3	Self-reported hours of oxygen* (within 24 hours)	x.xx (x.xx-x.xx)	x.xx
	Subgroup 4	Self-reported hours of oxygen* (within 24 hours)	x.xx (x.xx-x.xx)	x.xx

* Self-reported oxygen use is defined as mean hours/day. If missing, we will use mean h/day last week, using the questionnaire at 12 months, or (if missing) 3 months. (Duration=number of hours per day)

**t-test for mean difference

Table 12 Adverse events (PP and ITT)

Table 12.1 Adverse events

This table will be constructed if there is enough data.

	LTOT 15h/day n=	LTOT 24h/day n=	Total n=
Number of patients with AE (Total number of AE)	n[n]	n[n]	n[n]
Number of patients with SAE (Total number of SAE)	n[n]	n[n]	n[n]
Number of patients with possibly related AE (Number of possibly related AE)	n[n]	n[n]	n[n]
Number of patients with probably related AE (Number of probably related AE)	n[n]	n[n]	n[n]
Number of patients with unrelated AE (Number of unrelated AE)	n[n]	n[n]	n[n]
Number of AE with maximum intensity=MILD	n	n	n
Number of AE with maximum intensity=MODERATE	n	n	n
Number of AE with maximum intensity=SEVERE	n	n	n
Number of patients with maximum AE intensity=MILD	n	n	n
Number of patients with maximum AE intensity=MODERATE	n	n	n
Number of patients with maximum AE intensity=SEVERE	n	n	n

Table 12.2 Time to adverse events

		LTOT 15h/day n=	LTOT 24h/day n=	Total n=
Time to adverse events (all adverse events)	n			
	Mean (SD)			
	Median (IQR)			
	Min-Max			

2 Figures

NOTE: All figures below are based on dummy data

Figure 1 [Figures for inclusion over time](#)

Figure 1.1 Cumulative enrollment over time in the study (all randomized patients)

[figure not shown]

Figure 1.2 Cumulative enrollment over time in the study (by treatment)

If applicable

Figure 1.3 Cumulative enrollment over time in the study (by site)

If applicable

Figure 1.4 Cumulative enrollment over time in the study (by subgroup)

If applicable

Figure 1.5 Histogram with number of included patients by site and by treatment group

[figure not shown]

Figure 1.6 Reasons why the screened patients were not included in the study

[figure not shown]

Figure 1.7 Kaplan-Meier figure: Time from start until the patient stops being treated

A figure will be constructed and presented by treatment arm. Patients who stop being treated with oxygen before one year will be censored at this time.

Figure 2 CONSORT flow chart

* A patient is correctly randomized if he or she fulfills the inclusion criteria but not the exclusion criteria, has signed informed consent and has been randomized in Swedevox within four weeks of starting LTOT.

**All registry data available except for withdrawals

[figure not shown]
[figure not shown]

Figure 3 Cumulative hazard by treatment

Figure 3.1 Primary outcome (ITT)

[figure not shown]
Similar figures will be constructed for all primary and secondary outcomes (at 3 months and 1 year) presented by ITT, PP, Subgroups 1-4.

Figure 4 Kaplan-Meier figures

Kaplan-Meier figures will also be presented for all primary and secondary outcomes

Figure 5 HR with non-superiority limit for the primary endpoint

90% confidence intervals for HR_{24hvs.15h}, for the ITT, PP and subgroup populations. The p-value corresponds to the one-sided test, at 5% significance level, that the lower limit exceeds the hypothesized value 0.67.

Similar figures will be created for all secondary endpoints

3 Listings

[Listing 1](#) Patient disposition

[Listing 2](#) Demographics and characteristics at screening visit

Participant characteristics should also include center, population and randomized treatment group.

[Listing 3](#) Time of randomization to death or censoring

[Listing 4](#) Patients withdrawal

[Listing 5](#) Patients discontinuing LTOT

[Listing 6](#) Time of randomization to hospitalization or censoring

[Listing 7](#) Subjects excluded from the ITT and PP

[Listing 8](#) Screening failures

[Listing 9](#) Adverse events

[Listing 10](#) Loss to follow-up for the composite endpoint of death or 1st hospitalization

[Listing 11](#) Study termination (End of study)

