6.2 Per protocol (PP) population

A randomized patient will be excluded from the PP set if LTOT has been discontinued or the mean LTOT utilization during follow-up to the primary endpoint is below 20 h/day for the 24 h/day group, and below 13 h/day or above 17 h/day in the LTOT 15 h/day group. Self-reported oxygen utilization at 12 months, or if that is unavailable, at 3 months will be used for PP classification.

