7.7 Handling of missing data and data outside range

No imputation of missing data for variables used in the primary or secondary analyses will be performed. Only observed data will be used in the analyses.

If the date on a 3-month or 12-month form is either missing or unreadable we assume that the form was filled out at exactly 3 months or 12 months, respectively. For the PP analysis of the primary endpoint, the 3-month observation of self-reported oxygen utilization will be used if the 12-month observation is missing.

Data from forms submitted after hospitalization will not be used in the analysis of the primary outcome.

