*Socialstyrelsen will provide us with the date of event. Time to event (in days) will be calculated by UCR

*Time to composite event (All-cause mortality/ All-cause Hospitalization)	Included in the order from Socialstyrelsen
*Time to all-cause mortality	Included in the order from Socialstyrelsen
*Time to 1st hospitalization	Included in the order from Socialstyrelsen
Mortality from respiratory disease	respiratory disease or infection (A40; J00-J99)
Mortality from cardiovascular disease	Underlying cause of death (UCD) heart disease (I00-I99)
Hospitalization from respiratory disease	UCD respiratory disease or infection (A40; J00-J99)
Hospitalization from cardiovascular disease	UCD heart disease (I00-I99)
Time to Mortality from respiratory disease	Death (from respiratory disease) date – Study start date
Time to Mortality from cardiovascular disease	Death (from cardiovascular disease) date – Study start date
Time to Hospitalization from respiratory disease	Date of hospitalization from respiratory disease – Study start date
Time to Hospitalization from cardiovascular disease	Date of hospitalization from cardiovascular disease – Study start date
Time from start until the patient stops being treated	End of treatment – Date for start of treatment
Discontinued LTOT	From Swedevox Registry
Withdrawals	DATE_OF_LTOT_WITHDRAWAL REASON_W
ITT	All randomized patients that start LTOT
PP	A randomized patient will be excluded from the PP set if LTOT has been discontinued before the primary outcome assessment or the mean LTOT utilization during follow-up to the primary endpoint is below 20 h/day for the 24 h/day group, and below 13 h/day or above 17 h/day in the LTOT 15 h/day group
COPD	J44; exacerbation: J44.0 and J44.1
Heart disease	I00-I99
Respiratory disease or infection	A40; J00-J99
fev1/fvc	FEV1/FVC
BMI	WEIGHT(kg)/(HEIGHT (m)*HEIGHT (m))
Age	Round down (RANDOMIZATION_DATE - DATE_OF_BIRTH)/365.25
Duration of treatment	Number of days with treatment during the study
Self-rated hours of oxygen	Self-reported oxygen use (mean hours/24h) is categorized using 1) average use since starting LTOT, or (if missing) mean h/day last week; using the

	questionnaire at 12 months, or (if missing) 3 months (and the described algorithm used for each time point).
Subgroup 1 Participants with more severe resting hypoxemia at LTOT start	PaO ₂ < 7.4 kPa breathing air
Subgroup 2 Participants with more moderate hypoxemia at LTOT start	PaO ₂ 7.4–8.0 kPa breathing air

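### The 3-month per-protocol analyses use a PP set defined over the full year, so who is counted at month 3 depends on adherence in months 4 to 12

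*SAP*

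**What the plan says.** SAP section 6.2 excludes a patient from the PP set if LTOT was discontinued, or if "the mean LTOT utilization during follow-up to the primary endpoint is below 20 h/day for the 24 h/day group". In the other arm the limits are "below 13 h/day or above 17 h/day in the LTOT 15 h/day group". The source of the hours is fixed: "Self-reported oxygen utilization at 12 months, or if that is unavailable, at 3 months will be used for PP classification". The Derived variables list repeats the rule and dates the discontinuation criterion: a patient is "excluded from the PP set if LTOT has been discontinued before the primary outcome assessment". Section 7.5 puts the primary endpoint at day 365. Table 1 of the shells has a single PP row, and no 3-month PP set is defined anywhere.

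Sections 6 and 7.5 call for every endpoint to be analysed by both ITT and PP, and section 4.2.2 sets the secondary endpoints at 3 and 12 months. The shells follow: Table 5.2, "Table 5.14 Event rate at 3 months (PP", "Table 11.2 Secondary outcome (PP" and Table 9.2 (the parent tables of the last two have 3-month rows), and the 3-month PP row of Table 11.7.

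Section 7.7 adds: "Data from forms submitted after hospitalization will not be used in the analysis of the primary outcome".

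**The concern.** A PP analysis at 3 months should depend only on what happened up to month 3. Here membership uses information from after the analysis window. Someone who used the allocated hours for three months and stopped in month 8, or reported off-target hours at month 12, disappears from the 3-month PP tables. Someone who died in month 2 has no later behaviour to be judged on. The people removed are thus selected on having survived, and possibly on having stayed out of hospital.

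Section 6 states that ITT may not be conservative in this non-superiority design, so the PP results will be read as a check on ITT. The shells give two p-values per secondary outcome in Table 11, and plots against the non-superiority limit are planned for all secondary endpoints. A selection artefact in the 3-month PP column could be taken for an early treatment effect, or could hide one.

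**Working it through.** **Plan's own figure.** Section 9.2: n = ((1.645 + 0.842)/ln 1.5)² / (0.25 × 0.8) = 188.03, rounded up to 189, as stated. The planned total is 230, an allowance of 230 − 189 = 41 patients (17.8%) for PP loss.

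**3-month event proportion.** Input: 80% with an event at one year (section 9.2). Assumption: constant hazard. p = 1 − 0.2^0.25 = 0.331, or about 76 of 230 patients.

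**Model.** Let q be the share of patients compliant and event-free at month 3 who are later excluded, and f the share of 3-month events that cannot be excluded for later behaviour. Early-event patients who are not immune are assumed to be excluded at the same rate q.

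- Kept with event: E = p·[f + (1 − f)(1 − q)]
- Kept without event: N = (1 − p)(1 − q)
- PP risk r = E/(E + N); HR = ln(1 − r24)/ln(1 − r15)

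The documents give neither q nor f; the values below are assumptions.

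**Event proportion, all early events immune (f = 1).** The true value is 33.1%. With q = 10%, 20%, 30% and 40% it reads 35.5%, 38.2%, 41.4% and 45.2%. If all 41 planned losses came from the 154 patients event-free at month 3 (q = 26.7%), it would read 76/189 = 40.3%. That is an upper use of the allowance, which also covers patients already off target by month 3.

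**Hazard ratio, true HR = 1.**

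| Later exclusion, 24 h / 15 h | All early events immune (f = 1) | Only deaths immune, 40% of events | Only deaths immune, 10% of events |
|---|---|---|---|
| 20% / 20% | 1.00 | 1.00 | 1.00 |
| 20% / 35% | 0.85 (risks 38.2% vs 43.2%) | 0.92 (35.3% vs 37.6%) | 0.98 (33.7% vs 34.3%) |
| 35% / 20% | 1.18 | 1.08 | 1.02 |
| 10% / 30% | 0.82 | 0.91 | 0.97 |
| 5% / 10% | 0.96 | 0.98 | 0.99 |

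For all-cause mortality every event is immune. If deaths are 10% to 40% of the 33.1% (3.3% to 13.3% dead by month 3), the 20%/35% row gives an HR of 0.82 to 0.83, slightly further from 1 than 0.85 because the event proportion is lower.

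**Simulation** (20,000 trials, 115 per arm, follow-up cut at 3 months, f = 1). Equal removal leaves a true HR of 1.00 at 1.00 (26.7% removed per arm) and moves 0.67 only to 0.68 (20% per arm). Removal of 10%/30% gives 0.82 and 30%/10% gives 1.21 when the true HR is 1.

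**Which column applies.** The text supports two readings.

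- *Window to the 1-year assessment* (Derived variables). An early-hospitalised survivor who stops LTOT in month 8 is excluded too, and only deaths are immune.
- *Window to the patient's own event* (section 6.2, mean use up to the primary endpoint; section 7.7 on forms after hospitalisation). All early events are immune. But only 20/66.9 = 30% of patients event-free at month 3 reach month 12 event-free and can be judged on a 12-month form. Large values of q then become hard to reach without much discontinuation.

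**The case against.** The strongest counter-argument is that a reader might infer that the 3-month PP event rates are simply inflated and that HRs of 0.82 to 1.18 are to be expected. The SAP does not support that.

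- It does not say how a patient with no usable form is classified. The exclusion rule lists only reasons to remove, which suggests such patients stay. Section 7.7, however, says only observed data are used. If patients who die or are hospitalised before a 3-month form were dropped, early events would leave the set and the proportion would be deflated.
- The largest HR shifts combine the long exclusion window of one reading with the full immunity of the other. Taken consistently, each reading gives less for the composite.
- With equal removal the HR hardly moves. The limits differ in shape (two-sided in the 15 h arm, a floor only in the 24 h arm), which makes unequal removal plausible but says nothing about its direction.
- These are secondary PP results. The primary analysis is ITT at day 365.

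All four points stand, and they limit the size and direction of the effect. They do not remove it: under either reading, behaviour after month 3 can take a compliant patient out of a 3-month table. Sections 7.4 and 7.7 mention the 3-month fallback only for the PP analysis of the primary endpoint. If the whole rule were confined to that endpoint, the 3-month PP tables would have no definition at all, and the same repair would be needed. The Derived variables remark about applying the algorithm at each time point concerns how hours are read from a form, not PP membership.

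**Conclusion.** The point holds as a flaw in the secondary PP analyses. One PP set tied to the 1-year endpoint is used for 3-month outcomes, so membership depends on months 4 to 12. Deaths before month 3 are immune to later exclusion, and early hospitalisations are too if the window ends at the patient's own event.

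The direction of the distortion in event proportions depends on an unstated rule for patients without a form. The HR is biased only if later removal differs by arm, in a direction that cannot be known from the SAP. For the composite under 20% versus 35% later exclusion, the HR moves from 1 to between 0.85 (all early events immune) and 0.92 to 0.98 (only deaths immune, 10% to 40% of events). These figures rest on a constant hazard and on assumed exclusion and death shares. The primary ITT conclusion is not affected.

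**What to change.** Derive a second PP flag for all 3-month output, using only information up to the earlier of the patient's event and the 3-month cut-off: the LTOT withdrawal date from Swedevox, and hours from the 3-month form only. Keep the 12-month flag for 12-month output.

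State one rule, the same in both arms, for patients with no usable form before their event. One option is to keep them unless LTOT was discontinued before the event, with a sensitivity analysis that excludes them. Without this rule a 3-month flag would still leave early deaths and early hospitalisations unclassified.

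Label Tables 5.2, 5.14, 9.2, 11.2 and 11.7, and the matching figures, with the flag that applies, and add a second PP row to Tables 1 and 2.

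The cost is one extra derived variable, some SAP wording, and PP sets of different size at 3 and 12 months. No new data are needed, because section 5.7 already schedules withdrawal dates and self-reported hours at 3 months.
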